10.2 Screening assessments at Visit 1 (Week -2)

Patients with fibrotic ILD will be screened during their routine outpatient/inpatient assessment.

As part of routine clinical care, all patients will undergo:

- Physical examination (including demographics past and current medical history);
- Blood pressure;
- Pulse oxymetry at rest on room air;
- Spirometry and Echocardiogram
- Concomitant medication review;
- 6 Minute Walk Test (6MWT) - patients who desaturate $\leq 88\%$ on room air (RA) will have a repeat 6MWT on ambulatory oxygen, to assess optimal flow (7). 6MWT measured parameters will include 6-minute walk distance, oxygen saturation and heart rate Borg dyspnoea and Borg fatigue score before and at the end of the test, time to recovery of heart rate, oxygen saturation, Borg dyspnoea and Borg fatigue score, acceptable also +/- 1 week.;
- Collection of blood for laboratory analysis including BNP level. BNP levels are acceptable within +/- 1 month from visit 1;
- Pregnancy test (for women of child bearing potential).

Historical evidence will be acceptable for the purpose of study screening only if it was conducted within the timelines given below:

- The echocardiogram and the spirometry will be accepted if performed within 6 months before screening visit (visit 1). Where either of the assessments are not available as part of routine medical care the assessment should be booked to take place within 6 weeks post visit 1.
- The 6MWT will have to be performed at the screening visit +/- one week.
- BNP levels are acceptable within +/- 1 month from the visit 1.

Patients who desaturate $\leq 88\%$ will have a repeat 6MWT on ambulatory oxygen, to identify the oxygen flow needed to maintain optimal saturation ($\geq 90\%$, for at least half of the 6MWT duration, where possible) (7).

Patient should rest for at least 20 minutes between walks. The initial amount of oxygen offered will be calculated depending on level of desaturation during 6MWT on room air, as follows:

- Saturations 88-86% - start with 2 litres,
- Saturations 86-83% -start with 3 litres,
- Saturations 83-80% - start with 4 litres,
- Saturations 80-78% - start with 5 litres,

For saturations $< 78\%$, start with 6 litres and titrate up to and including 10 litres as required to achieve saturations of 90%, for at least half of the 6MWT duration, where possible.

Every 2 minutes of the 6MWT, the operator should consider increasing the O₂ flow, depending on saturation. If the saturation reached is between 87-89%, the flow should be increased by 1L/min, if < 87% by increments of 2L/min.

If SaO₂ is still < 88% for most of the walking test on 6L/min, a further 6MWT starting from 8L/min should be performed, using up to a maximum of 10L/min.

Oxygen saturation should be monitored for at least 3 minutes post walk and/or until saturation value has come back to pre-test value.

Patients expected to change treatment over the time course of the study, and those meeting criteria for long term oxygen therapy with SaO₂ at rest on room air < 94% will be excluded.

Patients with connective tissue disease-associated ILD or with sarcoidosis will be excluded if they have musculoskeletal involvement because of the potential impact of extrapulmonary involvement in day-to-day mobility, as will patients with significant communication or other locomotor difficulties, and/or severe co-morbidities, history of symptomatic ischaemic cardiac disease (exertion-induced chest pain) and anaemia (Hb < 9g/dl).

Patients included in the study will be given the K-BILD questionnaire during the screening visit to complete within 48h of the screening visit and to bring it back when attending Visit 2.

Patients included in the study will be given K-BILD questionnaire during the screening visit to complete within 48h of the visit and to bring it back at Visit 2 (Week 0) following the run in period.

10.3 Two weeks 'run in period'

Subjects will enter a two week run in period and those who fail to meet the eligibility criteria at the end of the run-in period will be withdrawn from the study.

10.4 Baseline assessments and Randomization (Visit 2 in Week 0)

Following the run-in period at the baseline visit (visit 2), stability of respiratory symptoms will be assessed according to routine clinical care. Only patients with stable symptoms (no chest infections and no changes in medications) during four weeks before including the run in period will be assigned in random order to two weeks on ambulatory oxygen or not treatment for two weeks.

Patients will be invited to perform two 6MWTs, one on oxygen and one on air-filled canisters at the flow rate identified during the first session, in random order, with a rest of at least 20 minutes between tests. Oxygen flow rates to be provided to the patient will be determined during the screening visit on the basis of the 6MWT on O₂, as the flow needed to provide and to maintain optimal oxygen saturation ≥ 90% for at least half of the 6MWT duration, where possible, and/or a maximal flow of 10L/min (7).

The patient will be blind to the content of the canisters.

Patients will then be randomised as to the order in which they will receive the portable oxygen *versus* no oxygen for the first two weeks of the treatment period as outlined in Section 9.2.

The treatment period of the study will consist of a four week randomized crossover trial of ambulatory oxygen for use during physical activity. At Visit 2, eligible patients will be asked to:

- complete the K-BILD questionnaire(14) (see “primary outcome” section) and three other questionnaires (the Shortness of Breath Questionnaire (SOBQ) (15), St George’s Respiratory Questionnaire (SGRQ) (16), Hospital Anxiety and Depression Scale (HDAS) (18), see below section 10.5);
- Concomitant medication review;
- Adverse Event
- Pulse oximetry at rest on room air
- 6MWT one on oxygen at the optimal flow rate identified during the screening visit
- 6MWT on air

The two 6MWTs (one on oxygen the other on air cylinder) will be undertaken in random order, with a rest of at least 30 minutes between tests. The patient will be blind to the content of the canisters. 6MWT measured parameters will include 6-minute walk distance, oxygen saturation and heart rate measured continuously (WristOx2™ model 3150), Borg dyspnoea and Borg fatigue score before and at the end of the test, time to recovery of heart rate, oxygen saturation, Borg dyspnoea and Borg fatigue.

- Provide a Sensewear armband for patients to wear during the second week (5+2 days) of each of the two week treatment periods;
- Provide oxymeter for patients to wear for 48 hrs during the second week of each two week treatment periods (on oxygen and on no oxygen);
- Supply a diary of daily activities and instructions on completion by patients during the two weeks until the next visit (Visit 3);
- Dispense treatment based on randomisation allocation.
- The next study visit will be set up within two weeks of the baseline visit.

10.5 Crossover Visit – Visit 3 in Week 2

At Visit 3, patients will be asked to:

- Pulse oximetry at rest on room air;
- Concomitant medication review;
- AE assessment;
- Global assessment of change in walking ability and breathlessness (18);

- Ask patients to submit daily activity diary relating to the previous two weeks, Sensewear armband given during the baseline visit (visit 2) and therefore related to the past two weeks;
- Ask patients to submit their 48 hrs oxymeter readings, provided at the baseline visit;
- Complete study questionnaires including K-BILD questionnaire (14), Shortness of Breath Questionnaire (SOBQ) (15), St George's Respiratory Questionnaire (SGRQ) (16), Hospital Anxiety and Depression Scale (HDAS) (18),
- Ask patients to complete diary of daily activities during the following two week treatment period until the next visit (visit 4);
- Provide Sensewear armband for patients to wear during the second week (5+2) of the two weeks of the final treatment period;
- Provide oxymeter for patients to wear for 48 hrs during the week when the Sensewear armband is worn;
- Cross-over to the alternative treatment.

10.6 End of Treatment Visit – Visit 4 in Week 4

At Visit 4, patients will be asked to undertake:

- Pulse oximetry at rest on room air
- Concomitant medication review
- AE assessment
- Global assessment of change in walking ability and breathlessness (19)
- Ask patient to submit daily activity diary, Sensewear armband, and 48 hrs oxymeter reading related to the final two week treatment;
- Complete study questionnaires including K-BILD questionnaire (14), Shortness of Breath Questionnaire (SOBQ) (15), St George's Respiratory Questionnaire (SGRQ) (16), Hospital Anxiety and Depression Scale (HDAS) (18).

10.7 Qualitative assessments

Qualitative assessment of impact of ambulatory oxygen will be undertaken *via* a semi-structured interview, with a purposive sample of 20 patients to investigate patients' and their carers' personal perspective on how the ambulatory oxygen has affected their day to day life. The interview will be conducted within 2 weeks of the end of treatment visit. Patients from the RBH site will be approached by the researcher at the end of treatment visit and asked if they will participate in the qualitative assessment. The PIS given to all patients at the beginning of the study is designed to explain the qualitative assessment aspect of the study. All patients recruited at RBH will be informed that the researcher will approach them during the last patient visit to ask if they wish to be interviewed to include their views of the impact of the ambulatory oxygen in the qualitative aspect of the study. If

the patient agrees a date will be agreed for the patient to be interviewed at a venue convenient to them (usually the patient's home).

During the interviews a semi-structured topic guide will address practical barriers to optimal oxygen usage, practical, social and psychological difficulties encountered, concerned about dependency, and views on the information required prior to ambulatory oxygen prescription. The interviews will also explore patients' (and carers') experience of participating in the trial. Notes will be written after each interview to aid reflexive analytical processes (20). Individual feedback on how the system and the service could be improved will assess how the needs of patients and their future involvement can be incorporated into the design of more patients and their future involvement can be incorporated into the design of more patients' centred devices.

Qualitative interview analysis: Interviews will be transcribed verbatim. Interview transcripts will be analysed thematically using a framework approach (21). Atlas/ti computer software (<http://atlasti.com>) will be used to manage and index the data prior to charting, mapping and interpretation.

10.8 Unscheduled Visits

Patients may require an unscheduled visit in addition to the regular scheduled protocol visits (*e.g.* symptoms of infection, worsening of disease, or assessment of AEs). If a patient requires an unscheduled visit, the study centre will be strongly encouraged to undertake the following assessments:

- Physical examination
- Vital signs
- AE review
- Concomitant medication review
- Lung function (spirometry and blood gas analysis)
- Collection of blood for laboratory analyses (to include full blood count)

10.9 Summary of study Assessments

Questionnaires: As previously stated, the primary outcome will be the change in the King's Brief Interstitial Lung Disease (K-BILD) total health status score (14). Participants will be asked to complete this questionnaire, at screening and baseline visit (Visit 1 and Visit 2) and at the end of each two-week period (visit 3 and 4). In the same points (visit 2, 3 and 4) they will also be asked to complete the Shortness of Breath Questionnaire (SOBQ - University of California, San Diego) (15), a widely validated index, designed to assess activity-related dyspnoea, as well as a questionnaire evaluating Quality of Life (St George Respiratory Questionnaire – SGRO) (16) and the Hospital Anxiety and Depression scale, both validated in ILD (18).

At the end of the third and fourth visit, participants will also be asked to make a global assessment of change in their walking ability and in their breathlessness on walking as “worse”, “about the same” or “better” (19), when compared to the previous two weeks.

Activity assessment: During the second week of each of the two week periods of the study treatment, patients will be asked to wear an activity monitor during waking hours, the Sensewear armband (Bodymedia - Pittsburgh, Pennsylvania), which measures energy expenditure, daily number of steps, and time spent at different levels of physical activity. Sensewear-derived measurements are sensitive and repeatable in chronic lung disease patients (22). The monitor is currently used at the RBH in a number of projects in COPD, and [name], one of this proposal's co-applicants, has established expertise in the use and assessment of activity measures. Patients will also be asked to complete a diary of daily activities as measure of physical activity, by using the modified diary method of Follick *et al* () (23, 24). Participants will be asked to complete this diary at least 3 times daily, recording the activity undertaken for the majority of each two hour block, in addition to specifying whether oxygen cylinders were used. In addition, total hours of outings each day will be recorded.

Oxygen Cylinder Use: will be expressed as number of cylinders used and as hours of use from self-reported data; patients will also be asked to write down the time of use of oxygen canisters for the two days a week when they will also be wearing the portable oxymeter, so as to correlate the two. At the end of the two weeks on oxygen, each patient will also be asked to fill in questionnaires about the number of cylinders fully and partially used and the number of unused cylinders.

Oxygen saturation: two days a week for each of the four weeks, patients will also be asked to wear a portable oxymeter, to assess oxygen saturation for 48 continuous hours. Measures of continuous oxygen saturation will also allow control for self-reported use of ambulatory oxygen.

10.10 Summary flow chart of study assessments

A summary chart of study assessments can be found in Appendix 1 of the study protocol.

11 Methods

11.1 Laboratory procedures

Blood samples will be taken at the start of the four week period including serum BNP levels. The measurement will be performed by the routine hospital laboratory within the trial sites as a standard clinical procedure in line with local policies and procedures. Copies of local reference ranges will be collected and the investigator must notify the CI of any subsequent changes in individual patient normalised values. These changes should also be recorded in the eCRF.

11.2 Radiology or any other procedure(s)

No additional x-rays, CT scans or exposure to radiation will occur as a result of taking part in this study.

11.3 Definition of the End of Trial

The end of the trial will coincide with the Last Patient Last Visit (LPLV).

12 Discontinuation/withdrawal of participants and stopping rules

As we do not expect there to be any toxicity from the use of ambulatory oxygen, subjects will be withdrawn from the trial only if they wish to do so. We will ask any patient who wishes to withdraw from the study, if they are willing, to fill in the relevant questionnaires at the end of the two and four week period, if needed *via* telephone, so as to be able to compare change in health status and other questionnaire related outcomes compared to baseline, against subjects completing the trial.

As our power calculations have allowed for subject withdrawals and incomplete data in a subset of patients, we do not expect the need to replace subjects, unless < 50 complete the study.

We do not envisage prematurely stopping the trial, again in view of the lack of toxicity of ambulatory oxygen in the patients selected for this trial.

13 IMPs and non-IMPs used in the trial

13.1 Name and description of each IMP

The IMP investigated in this study is medical oxygen (PL 15929/005), manufactured by Air Liquide Ltd. UK. Oxygen is a colourless, odourless gas with molecular weight 32, a boiling point of 183.1°C (at 1 bar) and a density of 1.355 kg/m³ (at 15°C and 1013mb).

Oxygen is present in the atmosphere at 21% and is an absolute necessity for life. Each of the four oxygen companies across the UK provide a light and a standard weight oxygen cylinder.

For the purpose of this study, we plan to use light-weight cylinders, which vary in weight from 1.8 kg (provided by BOC) to 2.2 Kg (provided by Dolby Vivisol and Air Liquide). We have decided to opt for the oxygen gas cylinders rather than the liquid oxygen counterparts, as the use of the former will allow an independent check on the number of oxygen cylinders used per week. This would not be possible using liquid oxygen, as the liquid oxygen contained in the cylinders evaporates over time even if not used by the patient, and there is no way for the investigators of independently counting the number of cylinders used, as the patient would fill in the liquid oxygen from a storage unit. Although there is the potential issue of difference in weight between the cylinders provided by Airliquide (which we expect would cover approximately 60% of our cohort, from a review of our referral patterns per UK region) and the other oxygen companies, we plan to adjust for cylinder weight in the analysis. Further, the relative weight of an oxygen cylinder will in any case vary widely depending on the height and weight of the patient and we plan to adjust for these variables in the analysis. Light weight cylinders across the different oxygen companies provide oxygen

flow rates from 0.5 to 15 L/min, lasting from 10 to 2 hours at a time depending on oxygen flow. Continuous oxygen flow *via* nasal cannulae will be used for all patients to standardize mode of delivery.

Ambulatory oxygen will be supplied by the relevant oxygen companies, on a Home Oxygen Order Form (HOOFF); the amount of oxygen required (hours per day) and flow rate should be specified. The supplier will determine the appropriate equipment to be provided. Special needs or preference will be specified on the HOOFF. The clinician will obtain patient's consent to pass on the patient's details to the supplier and the fire brigade. The supplier will contact the patient to make arrangements for delivery, installation, and maintenance of the equipment. The supplier will also train the patient to use the equipment. The supplier will continue to provide the service until the revised order is received or until notified that the patient no longer requires the home oxygen service.

Overall there are four oxygen companies which provide supplemental oxygen in the UK, including Air Liquide (which services North and South London, North and South West England, and the East Midlands), BOC (Eastern England and NorthEast), Baywater (Yorkshire and Humberside, West Midlands and Wales) and Dolby Vivisol (South Central England and South East Coast).

Source of IMPs including placebo

Ambulatory oxygen will be provided by the relevant oxygen companies in the UK based on the location of the patient participating in the study. It is currently confirmed that all three sites are in the region of the UK supplied by Air Liquide. However, the relevant oxygen company, dependent on the patient's post code, will be used as part of the standard clinical home delivery of ambulatory oxygen (*i.e.* BOC, Dolby Vivisol, and Baywater).

Ambulatory oxygen is also available on the drug tariff when a patient's home and social set up are appropriate. The most common portable flask is the Helios Marathon (H850) which can provide 1 - 6Lpm constant flow, or 1.5 - 4 on a pulsed delivery. The patients can refill the flask themselves. Liquid oxygen generally is lighter than portable gas cylinders.

Patients will also be supplied with a nasal cannula for oxygen delivery.

13.2 Accountability procedure for the IMPs

Ambulatory oxygen will be provided by the existing structure using the oxygen companies as described in Section 14.1 above. At the end of the study period, patients will continue on ambulatory oxygen as part of their standard care, and there will therefore be no returned IMP. If the patients are randomised to start on oxygen on the first two weeks of the four week trial period, the company will be asked to remove any unused oxygen cylinders prior the two weeks "off" oxygen.

To determine oxygen use during the study and in particular during the 2 weeks when patients are randomized to be on treatment, patients will be asked to keep a daily diary recording the number of hours spent using oxygen. The flow will be fixed at the optimal flow established at the baseline 6MWT on O₂ at the study entry. Investigators will also ask the relevant oxygen company to provide the number of cylinders delivered to the patient per

week along with the number of any unused cylinders at the end of the two weeks on oxygen, where possible.

The pharmacy hospital department will not be responsible for the provision and management of study IMP.

13.3 Route of administration, dosage, dosage regimen, and treatment period(s) of the IMPs

Ambulatory oxygen as provided by light weight portable oxygen cylinders, will be set up to provide an optimal oxygen flow rates established on study entry. The flow rate to be used for the individual patient will be the one identified in the baseline 6MWT on ambulatory oxygen, as the flow necessary to maintain optimal saturation during the walk test. We do not envisage that the flow rate will change during the two weeks of the trial.

13.4 Dosage modifications

As explained in more detail previously, the study will consist of two weeks on the ambulatory oxygen compared to two weeks without the portable unit. Should the patient require the change in flow rate this will be recorded in patients' notes and the CRF.

13.5 Assessment of compliance

Oxygen use will be expressed as number of full, half full and unused cylinders as self-reported by the patient after the two weeks on oxygen, which will be crossed checked by assessing accountability record provided by the relevant oxygen company.

To validate patient-reported use of oxygen cylinders, a research nurse at the Aintree site will sample 10 consecutive patients living in the nearby area. The research nurse will visit patients at home at the end of the two weeks of ambulatory oxygen to independently access numbers of fully used, half used and full oxygen cylinders. Comparison between patient and nurse reported cylinders use will be included in data analysis.

Patients will also be asked to fill in a daily oxygen use diary card to write down the time of use of oxygen canisters, and the activity being performed. This will be crossed check with the continuous oxygen saturation data recorded by the portable oxymeter, which they will be asked to wear for two days a week, so as to correlate the two.

13.6 Post-trial IMP arrangements

At the end of the trial, all patients will be offered to continue on ambulatory oxygen, as they would have been if they had not taken part in the trial.

13.7 Name and description of each non-IMP (NIMP)

Not applicable.

14 Pharmacovigilance

14.1 Definitions

Adverse Event (AE) — any untoward medical occurrence in a patient or clinical trial subject who is administered an IMP and which does not necessarily have a causal relationship with this treatment. (*i.e.* any unfavourable or unintended change in the structure (signs), function (symptoms), or chemistry (lab data) in a subject to whom an IMP has been administered, including occurrences unrelated to that product)

Adverse Reaction (AR) — any untoward and unintended responses to an IMP related to any dose administered (*i.e.* any unfavourable or unintended change in the structure (signs), function (symptoms), or chemistry (lab data) in a subject to whom an IMP has been administered and related to any dose administered)

Serious Adverse Event (SAE) or Serious Adverse Reaction (SAR)—any Adverse Event or Reaction in a trial subject that:

- Results in death; or
- Is life-threatening (places the subject, in the view of the Investigator, at immediate risk of death)
- Requires hospitalisation or prolongation of existing hospitalisation (hospitalisation is defined as an inpatient admission, regardless of length of stay; even if it is a precautionary measure for observation; including hospitalisation for an elective procedure, for a pre-existing condition)
- Results in persistent or significant disability or incapacity (substantial disruption of one's ability to conduct normal life functions)
- Consists of a congenital anomaly or birth defect (in offspring of subjects or their parents taking the IMP regardless of time of diagnosis).

Important medical events that may not be immediately life-threatening or result in death or hospitalisation but may jeopardise the subject or may require intervention to prevent one of the outcomes listed in the definition of serious will also be considered serious.

Suspected Unexpected Serious Adverse Reaction (SUSAR) — an Adverse Reaction which is classed in nature as both serious and unexpected.

An Unexpected Adverse Reaction is an Adverse Reaction, when both the nature and severity of the event is not consistent with the information about the medicinal product in question, as set out below:

- (a) in the case of a product with a marketing authorization, in the Summary of Product Characteristics (SmPC) for that product,
- (b) in the case of any other IMP, in the Investigator's Brochure relating to the trial in question.

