14.2 Terminology for classification of SAEs

A simple and brief description of **clinical symptoms** should be given using the following descriptions to record information about AEs:

1. Severity will be described using the following categories:

- **Mild**—the adverse event does not interfere with the volunteer’s daily routine, and does not require intervention; it causes slight discomfort.
- **Moderate**—the adverse event interferes with some aspects of the volunteer’s routine, or requires intervention, but is not damaging to health; it causes moderate discomfort.
- **Severe**—the adverse event results in alteration, discomfort or disability which is clearly damaging to health.

2. Relationship to treatment — the assessment of relationship of AEs to the administration of IMP is a clinical decision based on all available information at the time of the completion of the CRF. The following categories will be used:

- **Definitely** — there is clear evidence to suggest a causal relationship, and other possible contributing factors can be ruled out.
- **Probably** — there is evidence to suggest a causal relationship, and the influence of other factors is unlikely.
- **Possibly** — there is some evidence to suggest a causal relationship (e.g. the event occurred within a reasonable time after administration of the trial medication). However, the influence of other factors may have contributed to the event (i.e. the patient’s clinical condition, other concomitant events).
- **Unlikely** — there is little evidence to suggest there is a causal relationship (e.g. the event did not occur within a reasonable time after administration of the trial medication). There is another reasonable explanation for the event (*e.g.* the patient’s clinical condition, other concomitant treatments).
- **Not related** — there is no evidence of any causal relationship.
- **Not Assessable**

3. Expectedness will be described using following categories:

- **Expected** — an AE that is classed in nature as serious and which is consistent with the information about the IMP listed in the Investigator Brochure (or SmPC) **or clearly defined in this protocol.**
- **Unexpected** — an AE that is classed in nature as serious and which is not consistent with the information about the IMP listed in the Investigator Brochure (or SmPC).

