14.3.2 Serious Adverse Events (SAEs)

All SAEs will be recorded in the hospital notes and the eCRF.

All SAEs will be reported to the Sponsor *via* the Inform System on an SAE form unless otherwise stated in the protocol. The Chief or Principal Investigator will complete the Inform SAE reporting form and the form will be faxed to the RO on [name] or E-mailed to [contact], *via* Inform system within 24hrs of the Investigator becoming aware of the event.

The Chief or Principal Investigator (CI/PI) will respond to any SAE queries raised by the Sponsor as soon as possible.

Medical oxygen is licensed in the UK and will be used within its marketing authorization in this study. The most up to date version of the SmPC will be used as the IMP reference document for this study.

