14.3.4 Expected SAE/Rs related to IMP

Expected Adverse Reactions are known side effects of the IMP reported in SmPCs of Medicinal Oxygen.

Ambulatory oxygen therapy is usually associated with only mild side effects, which may include nasal mucosa dryness or skin irritation from the nasal cannula.

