14.6 Reporting to Regulatory Authority

The RO will notify all SUSARs to the MHRA electronically *via* e-SUSARs Database and the main REC using the CIOMS form. The CIOMS form should be completed by the CI and PI at each site and sent to the RO as described in Section 15.3.2 of the protocol.

The RO will inform the MHRA and the main REC of fatal or life threatening SUSARs as soon as possible, but no later than 7 calendar days after the RO receives the SAE report form. Any additional information will be reported within 8 days of sending the first report.

The RO must report all other SUSARs and safety issues to the MHRA and main REC, as soon as possible but no later than 15 calendar days after the RO has first knowledge of the minimum criteria for expediting reporting.

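### Protocol sections 14.1 and 14.2 define 'unexpected' differently, and the narrower 14.1 wording governs which serious reactions count as SUSARs

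*Protocol*

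**What the plan says.** Protocol section 14.1 (Definitions) gives the rule: "An Unexpected Adverse Reaction is an Adverse Reaction, when both the nature and severity of the event is not consistent with the information" in the SmPC for an authorised product, or in the Investigator's Brochure for any other. The same section defines a SUSAR as "an Adverse Reaction which is classed in nature as both serious and unexpected".

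Section 14.2, which supplies the categories for classifying events, describes an unexpected event as "an AE that is classed in nature as serious and which is not consistent with the information about the IMP" in the Investigator Brochure or SmPC. It does not mention nature and severity as separate tests. Its Expected category also admits events that the protocol itself clearly defines. The Unexpected category has no matching exception.

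Section 14.3.2 fixes the reference: "The most up to date version of the SmPC will be used as the IMP reference document for this study". Section 14.3.4 says that expected reactions are those reported in the SmPC, and adds: "Ambulatory oxygen therapy is usually associated with only mild side effects, which may include nasal mucosa dryness or skin irritation from the nasal cannula".

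Section 14.6 attaches the consequence: "The RO will notify all SUSARs to the MHRA electronically", and also to the main REC. The limits are 7 calendar days for fatal or life-threatening cases and 15 for the others.

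**The concern.** One term has two tests, and the protocol does not say which governs. The stricter test sits beside the only definition of a SUSAR, so it decides which suspected serious reactions are sent on under the expedited timelines. The looser test is the one investigators meet when they classify an event.

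An investigator working from 14.2 could mark an event unexpected, and a reviewer checking it against 14.1 could then conclude that it is not a SUSAR. Two people applying the protocol correctly could reach opposite answers on the same event. At stake is whether the regulator and ethics committee hear of it promptly.

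**Working it through.** No figure in the plan bears on this point, so the check is a comparison of the two definitions.

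**Inputs.** The 14.1 test for unexpected; the 14.1 SUSAR definition; the 14.2 test for unexpected; the SmPC as reference (14.3.2); the reporting rules in 14.4, 14.4.1 and 14.6.

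**Step 1. Classify a suspected serious adverse reaction.** Seriousness and suspected causality are taken as given, so only expectedness decides whether it is a SUSAR. Section 14.1 is read literally and 14.2 on its plain reading, under which an inconsistency in either respect is enough.

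| Nature against SmPC | Severity against SmPC | Section 14.1 | Section 14.2 |
|---|---|---|---|
| consistent | consistent | not unexpected | not unexpected |
| consistent | not consistent | not unexpected | unexpected |
| not consistent | consistent | not unexpected | unexpected |
| not consistent | not consistent | unexpected | unexpected |

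Section 14.1 gives 1 unexpected combination of 4, and section 14.2 gives 3 of 4. They disagree on 3 − 1 = 2, the two mixed rows. These are counts of logical combinations, not frequencies of events.

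**Step 2. An illustration of the second row.** Section 14.3.4 names skin irritation from the cannula among effects that are usually mild. Suppose such a reaction were severe enough to need admission, and suppose the SmPC lists it only in a mild form (an assumption, since the SmPC is not at hand). Its nature is listed, so the first half of the 14.1 condition fails and it cannot be a SUSAR there. Under 14.2 its severity makes it inconsistent with the reference, so it is unexpected.

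**Step 3. Follow the reporting route.** Under 14.4(b) every SAE or SAR, expected ones included, goes on the eCRF within 24 hours, the Research Office is notified, and the CI or designee reviews it within 2 working days. That step does not depend on expectedness. Under 14.4.1 the CI or designee then checks that a reported SUSAR really is one, and 14.6 ties expedited notification to that label. The 14.1 wording therefore takes effect at the check and at onward notification.

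**Step 4. Compare with the protocol's own usage.** Section 14.3.5 lists disease progression as expected. Sections 14.3.1 and 14.4(e) tell the investigator to report progression as unexpected if the product is suspected of having made it faster. There the kind of event is one the protocol expects and only its course differs. That fits an either/or test and not the 14.1 test.

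**The case against.** **The wording may be loose drafting.** The 14.1 sentence can be read charitably as requiring consistency in both respects, which is the either/or rule, and 14.2 can be read as shorthand for 14.1. Both readings are possible. But they pull in different directions on which test applies, and a definition that starts a reporting clock should not need a charitable reading.

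**The sponsor learns of every serious event anyway.** This stands, and it limits the consequence: no serious reaction goes unrecorded, and the CI's review lowers the risk that sites differ. It does not restore onward notification, because the term applied in that review is the one 14.1 defines. Section 14.6 also sends on other safety issues, but gives no criterion for them. The sponsor's pharmacovigilance SOP (14.3) and the Clinical Trials Regulations (section 25) may apply a sound rule in practice. The protocol does not say that either overrides its definitions.

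**The third row may be empty.** If a reaction of unlisted nature has no listed severity to agree with, its severity might always count as inconsistent. The disagreement would then shrink to the second row, which does not depend on this argument.

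**A stronger reading that fails.** A reader might infer that every serious reaction of a listed nature differs from the SmPC in severity and so falls into the gap. The documents do not support that. The SmPC is not shown and may list graver reactions; 14.3.4 says only that side effects are usually mild; and seriousness is not severity. Section 14.1 counts any inpatient admission as serious, even a precautionary one, so a reaction of listed nature and listed severity can be serious and properly expected. Nor does the test concern use outside the licence: it concerns agreement with the reference document, and 14.3.2 says the oxygen is used within its authorisation.

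**Conclusion.** The point holds as a contradiction between two definitions in the protocol. Read literally, 14.1 excludes from SUSAR status a suspected serious reaction that is inconsistent with the SmPC in one respect only. Section 14.2, read plainly, includes it.

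The practical effect is confined to expedited notification to the MHRA and main REC. How many events would be affected cannot be derived from the protocol. With 80 planned patients, each having two weeks on oxygen, the number is probably very small. Sample size, power and the K-BILD analysis are untouched. The conclusion rests on the literal wording of 14.1 and the plain reading of 14.2. It does not depend on what the SmPC lists, although the number of reactions falling in the gap does. It deserves correction because the stated rule gives a wrong classification when followed and the remedy is cheap.

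**What to change.** In section 14.1, replace the requirement that nature and severity both be inconsistent with the reference information by a requirement that the nature or the severity be inconsistent. In section 14.2, drop the separate description of Unexpected and refer to 14.1, so that one definition governs both the form and the SUSAR decision.

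The same edit should say how the Expected category's allowance for events defined in the protocol applies. As worded, an event listed in 14.3.5 but absent from the SmPC meets both the Expected and the Unexpected descriptions in 14.2. The text should state whether that allowance bears on the SUSAR decision or only on disease-related events, and should fit the instruction on faster progression in 14.3.1 and 14.4(e).

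The cost is a short protocol amendment covering two sections. No data collection, form field or analysis has to change because of the definition itself. At most, a few more events would be assessed for expedited reporting.
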